3. To measure VE using other outcome measures such as against all episodes of *Pf malaria with symptoms* and *Pf malaria* rather than against the first episode, using proportional analysis, or using ITT or ATP populations, or severity of malaria infections or hemoglobin concentration.
4. To explore the relationship between detectable parasitemia prior to vaccination and VE.

Endpoints:

Primary Endpoints:

1. Proportion of vaccinees compared to controls experiencing related SAEs from V1 to 26 weeks after V3
2. VE computed as one minus the estimated hazard ratio (HR) (time-to-event analysis) for first episode of *Pf malaria with symptoms* from 2 weeks after V3 to 26 weeks after V3 in the modified ITT (mITT) population.

Secondary Endpoints:

1. Safety and tolerability in children
 - The differences in proportions of vaccinees compared to controls experiencing unsolicited AEs from the time of V1 to 14 days after V3 (or last immunization).

- The differences in proportions of vaccinees compared to controls experiencing laboratory abnormalities from time of V1 to 14 days after V3.
- The differences in proportions of vaccinees compared to controls experiencing solicited Aes during the 7 days following each immunization.
- 2. VE computed as one minus the estimated hazard ratio (HR) for first episode of *Pf malaria* detected by thick blood smear (TBS), from 2 weeks after V3 to 26 weeks after V3 in the mITT population.
- 3. Antibody levels to PfCSP by standardized ELISA comparing protected and unprotected vaccinees and controls.

Exploratory Endpoints:

- 1. Humoral and cellular immune responses to PfSPZ Vaccine
- 2. Genotyping of peripheral blood Pf parasites
- 3. Additional measures of VE
 - VE against all episodes (rather than first episode) of *Pf malaria with symptoms* and *Pf malaria* by Cox regression analysis
 - VE computed by proportional (binary) analysis (1 – risk ratio) for first episode of *Pf malaria* detected by TBS, from 2 weeks after V3 to 26 weeks after V3 in the intention-to-treat (ITT), mITT and according to protocol (ATP) populations (whole group and subgroups)
 - VE computed as one minus the estimated HR for first episode of *Pf malaria* detected by TBS, from 2 weeks after V3 to 26 weeks after V3 in the ITT and ATP populations (whole group and subgroups)
 - VE for *Pf malaria* measured by and nucleic acid detection in children from 2 weeks after V3 to 26 weeks after V3 using both (time to event, proportional/binary)

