5. STUDY DESIGN

5.1 OVERALL DESIGN

This phase 2 study will enroll healthy Malian children between 6 and 10 years of age residing in Bancoumana and surrounding villages to participate in a randomized, double blind, placebo-controlled study to assess the safety, immunogenicity and protective efficacy of PfSPZ Vaccine. Participants will be immunized with a 3-dose series of 9.0×10^5 PfSPZ of PfSPZ Vaccine or normal saline (placebo) at 1, 8, and 29 days. Subjects will be screened for eligibility for enrollment. Enrollment will begin with AL dosing approximately 4 weeks prior to their first dose of vaccine. Volunteers will be randomized into two arms (1 vaccine arm, 1 control arm) in a 1:1 ratio.

Vaccinated subjects and controls will then be followed for safety and assessment for malaria infection during the subsequent malaria transmission season.

~268 children between the ages of 6 and 10 years old inclusive will be enrolled as follows:

Arm 1 (PfSPZ Vaccine): (n = ~134) children ages 6 – 10 will receive three doses of PfSPZ Vaccine (9.0×10^5 PfSPZ) via direct venous inoculation (DVI) at 1, 8, and 29 days

Arm 2 (normal saline): (n = ~134) children ages 6 – 10 will receive normal saline via DVI at 1, 8, and 29 days

All subjects will receive artemether-lumefantrine (AL) approximately 1-4 weeks before the first and third dose of PfSPZ Vaccine or normal saline for clearance of *Pf* parasitemia.

NB.: the second round of AL clearance prior to third vaccinations may or may not proceed depending on the timing of the beginning of the rainy season and the timing of malaria transmission in the community and will be decided by the Mali PI.

Vaccinated participants and non-vaccinated controls will be monitored for development of *Pf malaria with symptoms* and *Pf malaria* (parasitemia) through the natural malaria transmission season to estimate vaccine efficacy (VE). During the surveillance period, both active and passive surveillance will be used to identify *Pf malaria with symptoms* (see section 9.7). Blood smears will be made at any time a participant presents with a clinical syndrome consistent with malaria and read in real time, with all infections treated. Twenty-eight days later, these subjects will resume surveillance to make it possible to count all episodes of malaria with symptoms (exploratory objective). Parent/guardians will be encouraged to report to the clinic any time that a child is ill.

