In addition, blood smears will be made every four weeks in all participants as active surveillance for *Pf malaria* (parasitemia). However, to avoid confounding the primary clinical endpoint, these blood smears will be reported retrospectively at the end of the primary surveillance period.

This study will not interfere with routine standard-of-care for children. Participants will receive medical care through the local health clinic, including standard immunizations and seasonal malaria chemoprophylaxis if indicated, per the standard of care in Mali. The study will support the clinics by providing acute care assessments, ensuring supply of RDT and blood smears for malaria diagnosis, drugs for malaria treatment and prevention, and neurodevelopmental screening. During the study visits, the team will encourage families to continue consistent follow-up with their pediatric providers and will coordinate any acute care in consultation with the local pediatrician as needed.

Indoor residual spraying (IRS) is performed in only about 3 of the 75 districts in Mali, and this does not include Bancoumana. Therefore, it is not expected that IRS will affect outcomes in this study. In 2018, bednet use was 82.2% in the Koulikoro region of Mali where Bancoumana is located. It is expected that randomization will balance out bednet use between the study groups. However, participants will be evaluated at routine visits with regard to bednet use, so that a subgroup analysis can be performed taking bednet use into consideration.

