9.7 CLINICAL EVALUATIONS

Complete physical examination: (e.g., height and weight, heart rate, organ systems, or other functional abilities).

Electrocardiograms (EKGs): Electrocardiograms (12-lead ECGs) will be performed during screening and as needed throughout the study by the study site team in Mali and read by a Mali cardiologist if needed. Subjects with QT interval (QTc) > 460 ms will be excluded as AL may prolong QTc. Subjects with clinically significant abnormalities will also be excluded from the study.

Malaria blood smears: The gold standard for malaria diagnosis and evaluation of VE endpoints is the detection of malaria parasites on Giemsa-stained thick blood films. Blood smears are prepared in duplicate according to standard malaria challenge procedures and evaluated by trained study microscopists, and the results reported to the study PI. At least 0.5 μ L are scanned for the presence of malaria parasites. This method allows for detection of a parasite density of approximately 2 parasites/ μ L and early diagnosis, often before subjects become symptomatic for malaria. Slides are considered positive if at least one unambiguous *P. falciparum* parasite per slide are identified and confirmed by a second microscopist.

When venipuncture is performed, thick blood smears will be prepared from the blood remaining in the IV cannula or needle, or (at time points when no IV blood collection is planned) from a finger prick sample. The smears will be examined microscopically.

Thick blood smears will be used for diagnosis throughout the study.

Passive and active case detection: Contact information for the study clinic and principal investigator will be provided to the parent/legal guardian of all participants so they will be able to easily schedule a clinical evaluation for any symptoms of concern experienced by the study participant. Study participants are also welcome as walk-ins at the study clinic. Parents or guardians will be actively encouraged throughout the trial to report to the clinic whenever a participant is ill.

In addition, active outreach to study subjects will occur no less frequently than every two weeks during the malaria surveillance period. Parents / participants will be questioned at these visits for history of malaria symptoms including subjective fever, and body temperature will be assessed at each encounter (see Table 13).

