10.4 STATISTICAL ANALYSES

10.4.1 General Approach

Missing Data

Subjects who discontinue early or are lost to follow-up will be censored from applicable analyses at the last date where the study outcome can reliably be determined (e.g., date of last available TBS specimen without parasitemia).

It is anticipated that some event dates required for safety analyses may be incomplete. If the event onset day is unknown, then the date will be imputed as the last date the subject could reliably be assumed to be event free (e.g., the previous study visit where the event was not reported). If the resolution day is incomplete, then the date will be imputed as the date that the event was reliably known to no longer be present.

It is anticipated that some TBS results will be missing. In those instances where one TBS is missed, the result will be imputed to be the same as the result of the next TBS. Up to three such single missing TBS will be allowed in a research subject during the 26 weeks of follow-up without disqualifying the participant from the ATP population (as long as the individual meets other requirements for ATP, such as receiving all three immunizations within the correct time windows). If there are situations where two or more consecutive TBS are missed, the result will again be imputed to be the same as the result of the next TBS, and the research subject will be included in the m-ITT population (as long as the individual meets other requirements for m-ITT, such as receiving all three immunizations). If the only TBS missed is the last, there will be no imputation, the missing data point will be ignored, and the individual may be included in the ATP population. If the two or more TBS missed are the last, there will be no imputation, the missing data points will be ignored, and the individual may be included in the m-ITT population. However, if more than the last two TBS are missed, the individual will not be included in proportional efficacy analyses, although may be included in time-to-event efficacy analyses.

Multiple Testing

The primary VE endpoint is the VE against *Pf malaria with symptoms*. The overall vaccine efficacy will be assessed over all participants.

No multiplicity adjustment will be made for secondary efficacy or safety endpoints.

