3.4 Handling of missing Data

It is anticipated that some event dates required for safety analyses may be incomplete. If the event onset day is unknown, then the date will be imputed as the last date the subject could reliably be assumed to be event free (e.g., the previous study visit where the event was not reported). If the resolution day is incomplete, then the date will be imputed as the date that the event was reliably known to no longer be present.

It is anticipated that some TBS results will be missing. In those instances where one TBS is missed, the result will be imputed to be the same as the result of the next TBS. Up to three such single missing TBS will be allowed in a research subject during the 26 weeks of follow-up without disqualifying the participant from the ATP population (as long as the individual meets other requirements for ATP, such as receiving all three immunizations within the correct time windows). If there are situations where two or more consecutive TBS are missed, the result will again be imputed to be the same as the result of the next TBS, and the research subject will be included in the mITT population (as long as the individual meets other requirements for mITT, such as receiving all three immunizations). If the only TBS missed is the last, there will be no imputation, the missing data point will be ignored, and the individual may be included in the ATP population. If the two or more TBS missed are the last, there will be no imputation, the missing data points will be ignored, and the individual may be included in the mITT population. However, if more than the last two TBS are missed, the individual will not be included in proportional efficacy analyses, although may be included in time-to-event efficacy analyses.

Subjects who discontinue early or are lost to follow-up will be censored from applicable analyses at the last date where the study outcome can reliably be determined (e.g., date of last available TBS specimen without parasitemia).

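### The exploratory proportional (1 − risk ratio) VE drops children on late smear attendance, even when their malaria event has already been observed

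*SAP*

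**What the plan says.** The Exploratory Endpoints in the protocol synopsis include "VE computed by proportional (binary) analysis (1 – risk ratio) for first episode of" *Pf malaria* detected by thick blood smear, "from 2 weeks after V3 to 26 weeks after V3 in the intention-to-treat (ITT), mITT and according to protocol (ATP) populations". Proportional analyses are also listed there for symptomatic malaria at other parasite densities.

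SAP section 3.4 and protocol section 10.4.1 (Missing Data) treat missing final smears in the same way. If only the last smear is missed, nothing is imputed and the child may be in the ATP population. For longer gaps at the end: "If the two or more TBS missed are the last, there will be no imputation, the missing data points will be ignored", and the child may be in the mITT population. Beyond two, the SAP says: "However, if more than the last two TBS are missed, the individual will not be included in proportional efficacy analyses". The protocol has the same rule: "the individual will not be included in proportional efficacy analyses, although may be included in time-to-event efficacy analyses". I read this last rule as three or more smears missed at the end of follow-up.

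Two features of the design matter here. Protocol section 5.1 says "blood smears will be made every four weeks in all participants as active surveillance for" parasitemia, and Table 2 runs that schedule to Day 211. Children treated for an episode stay under observation: "Twenty-eight days later, these subjects will resume surveillance to make it possible to count all episodes of malaria with symptoms".

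**The concern.** In a binary analysis a child's outcome is fixed once the event has been observed. Smears missed afterwards carry no further information about it. The rule nevertheless uses those smears to decide whether the child is analysed, and makes no exception for a recorded event. Because surveillance continues after an episode, such children will exist.

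The rule works differently for a child with no event. One who misses the last three smears is removed. One who misses exactly the last two is kept. The text says only that the gaps are ignored and that exclusion starts above two, so the status of that child is an inference, but a binary risk has no place for the child except as event-free through week 26. SAP section 3.4 also censors early leavers in applicable analyses, but a crude risk ratio cannot censor.

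The result is neither a complete-case risk nor a censoring-adjusted one. Observed endpoints are lost, and the risk ratio is biased if attendance after an event differs from attendance without one.

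**Working it through.** **Plan's own figure.** No stated figure depends on the missed-smear rule. The nearest is Table 15: 82% power with 120 per arm, control risk 0.35, VE 0.5 and 10% dropout (protocol section 10.2).

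- HR = ln(1 − 0.175)/ln(1 − 0.35) = 0.4466
- Events = 120 × 0.90 × (0.35 + 0.175) = 56.7
- Freedman log-rank: z = √56.7 × (1 − 0.4466)/(1 + 0.4466) − 1.96 = 0.92, so power is 82.1%

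The table reproduces. It concerns the log-rank test and does not change. Enrolment of about 134 per arm (same section) is used below.

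**The gap.** Four-weekly smears fall on Days 43, 71, 99, 127, 155, 183 and 211. A child missing the last two was last seen by smear on Day 155, which is (155 − 29)/7 = 18 weeks after V3. That leaves 26 − 18 = 8 of 24 weeks (33%) without a scheduled smear.

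**How many children and events.** Assumption: 10% leave, evenly over Days 43–211 (168 days), independently of outcome, with flat event timing.

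- Excluded (left before Day 155): 10% × 112/168 = 6.7%, or 0.067 × 134 ≈ 9 per arm.
- Events observed and then discarded (event first, then leaving, before Day 155): 10% × ½ × (112/168)² = 2.2% of all events. Observed events are 0.90 + 0.10 × ½ = 95% of all events, so 2.2/95 = 2.3% of observed events are lost. Simulation gives about 2.5%.
- At control risk 0.35 that is 0.025 × 0.35 × 134 ≈ 1.2 control events and 0.025 × 0.175 × 134 ≈ 0.6 vaccine events. At an assumed control risk of 0.60 with VE 50% it is about 2.0 and 1.0.
- Kept as event-free after missing exactly two: leaving between Days 155 and 183 is 10% × 28/168 = 1.7%, less those who already had an event. Simulation gives about 1.0–1.5%, or 1–2 children per arm.

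**Bias when cases and non-cases leave at different rates, the same in both arms.** With true risk p in an arm and exclusion probabilities d1 (cases) and d0 (non-cases), the analysed risk is p(1 − d1)/[p(1 − d1) + (1 − p)(1 − d0)]. True VE is set at 40%; d1 and d0 are assumptions.

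| d1 vs d0 | control risk 0.35 | 0.50 | 0.80 |
|---|---|---|---|
| 20% vs 10% | 41.0% | 41.4% | 42.3% |
| 30% vs 10% | 42.0% | 42.9% | 44.8% |
| 10% vs 20% | 39.0% | 38.6% | 37.7% |

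For example, at 0.50 with 20% vs 10%: controls 0.40/0.85 = 0.4706, vaccinees 0.24/0.87 = 0.2759, VE = 41.4%. The shifts run from 1.0 to 4.8 points.

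**Simulation of the literal rule.** 1,000,000 children per arm, seven smears, true 1 − RR of 50%, control risk 0.35 or 0.60, event timing flat or peaked. All attrition patterns are assumptions.

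| Attrition | Literal rule | Kaplan-Meier |
|---|---|---|
| 10–20%, unrelated to outcome | 49.7–50.4% | 49.7–50.3% |
| 10% plus 10% of cases leaving after the event, both arms | 50.5–51.2% | 49.8–50.1% |
| 10% plus 20% of cases leaving after the event, controls only | 44.7–47.2% | 49.8–50.3% |
| 10% plus 20% of cases leaving after the event, vaccinees only | 54.2–56.3% | 49.8–50.3% |

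Adding back observed cases while still dropping event-free early leavers is not a clean repair. It selects on outcome: with dropout unrelated to outcome it gave 48.5–50.5%, and it pushed a true control risk of 35% up to 35.2–36.2%.

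**The case against.** The strongest reply is that little depends on this. Proportional VE is exploratory, and the rule itself leaves time-to-event analyses open to the excluded children. SAP sections 3.2.1 and 3.2.2 already plan Kaplan-Meier cumulative probabilities through week 26 for both endpoints. The shifts are small beside sampling error: with 108 evaluable per arm (120 × 0.90), the 95% CI around a VE of 40% is roughly 6–62% at control risk 0.35 and 25–52% at 0.80. All of this stands and limits the point to a minor one.

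It can also be said that the final eight weeks are not unobserved, because "active outreach to study subjects will occur no less frequently than every two weeks during the malaria surveillance period". That holds for symptomatic malaria. It does not hold for *Pf malaria* with or without symptoms, where asymptomatic parasitemia is found on the scheduled smears, which are the ones missed.

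Some stronger readings are tempting, and the documents do not support them:

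- A reader might infer from 10% dropout that about 10% of observed cases are lost. A discarded case must have an event, then leave, then miss at least three smears, which gives about 2–2.5%.
- A reader might take the problem to run equally through ITT, mITT and ATP. Children missing two or more final smears are assigned to mITT, so ATP is largely spared.
- A reader might suppose that a comparison with earlier trials is planned on this scale. Earlier proportional results appear only as background in protocol sections 3.2.2 and 5.2.3.

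**Conclusion.** The point holds as a minor one. As written, the rule can delete known cases from the exploratory proportional VE because of attendance after the outcome, and it keeps some children with an eight-week gap in smears as event-free. The first part rests on the absence of an exception in the text, the second on inference from the cut-off. It mainly concerns ITT and mITT. Primary and secondary VE and the Table 15 power are untouched.

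The size depends on dropout patterns that the documents do not give. Unrelated to outcome, the bias is under 0.5 points and the cost is roughly one observed event per arm at control risk 0.35. Related to outcome but alike in both arms, it is about 1–5 points. The 3–6 point range needs 20% of cases to leave after their event in one arm only, which double blinding makes less likely. It is an outer range and not an expectation.

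**What to change.** In both SAP section 3.4 and protocol section 10.4.1, delete the sentence that excludes children from proportional analyses. Define proportional VE as 1 minus the ratio of the Kaplan-Meier cumulative probabilities at 26 weeks after V3. Include all children in the given population, keep every observed event, censor event-free children at the last evaluable smear, and give a 95% CI calculated on the log scale.

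A crude 1 − RR that keeps all observed events may be reported as a sensitivity analysis, provided the text states how event-free children with missing final smears are counted.

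No new data, visits or participants are needed. The Kaplan-Meier estimates are already planned in SAP sections 3.2.1 and 3.2.2 for mITT; the same code would be run for the other populations and case definitions. The cost is a wording change in two documents, made before unblinding and disclosed in the study report as protocol section 10 requires. Kaplan-Meier still assumes that children who leave event-free are like those who stay, so reasons for leaving should be tabulated by arm.
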